6.3.4.5. Renal Adverse Events

Elevated creatinine and biopsy-confirmed tubulointerstitial nephritis and allergic nephritis have been infrequently observed following treatment with anti-PD-1 therapies. Physicians should monitor creatinine regularly (see [Table 20](#)).

Table 20: Management of Renal Adverse Events

For guidelines for delaying a dose, refer to Section 6.3.2 .	
Grade 1	Monitor creatinine weekly Creatinine returns to baseline: continue monitoring per protocol Creatinine increases: treat as Grade ≥ 2
Grade 2-3	Monitor creatinine every ≤ 3 days Immediately: start 0.5-1.0 mg/kg/d methylprednisolone IV or oral equivalent; consider prophylactic antibiotics; consider renal biopsy Improvement to Grade ≤ 1: taper steroids over at least 4 weeks Persistence >7 days or worsening: treat as Grade 4
Grade 4	Monitor creatinine daily Immediately: consult nephrologist; consider renal biopsy; start 1.0-2.0 mg/kg/d methylprednisolone IV or IV equivalent; add prophylactic antibiotics Improvement to Grade ≤ 1: taper steroids over at least 4 weeks
General	Subjects on IV steroids may be switched to an equivalent dose of oral corticosteroids (eg, prednisone) at start of tapering or earlier, once sustained clinical improvement is observed. The lower bioavailability of oral corticosteroids needs to be considered.

6.3.4.6. Neurological Adverse Events

Neurological AEs have been uncommonly observed following treatment with anti-PD-1 therapies. Neurological AEs can manifest as central abnormalities (eg, aseptic meningitis or encephalitis) or peripheral sensory/motor neuropathies (eg, Guillain-Barre Syndrome). The onset has been observed as early as after a single treatment. Early recognition and treatment of neurologic AEs is critical to their management (see [Table 21](#)). Subjects should be advised to seek medical evaluation if they notice impairment in motor function (eg, weakness), changes in sensation (eg, numbness), or symptoms suggestive of possible central nervous system abnormalities such as new headache or mental status changes.

Table 21: Management of Neurological Adverse Events

For guidelines for delaying a dose, refer to Section 6.3.2 .	
Grade 1	Monitor per protocol Worsening: treat as \geq Grade 2
Grade 2	Immediately: treat symptoms according to institutional standards; consider 0.5-1.0 mg/kg/d methylprednisolone IV or oral equivalent Worsening: treat as Grade 3-4.
Grade 3-4	Immediately: consult neurologist; treat symptoms according to institutional standards; start 1.0-2.0 mg/kg/d methylprednisolone IV or IV equivalent; prophylactic antibiotics Worsening or atypical presentation: consider immunoglobulins IV (IVIG) or other immunosuppressive therapies according to institutional standards Improvement to \leq Grade 2: taper steroids over at least 4 weeks
General	Subjects on IV steroids may be switched to an equivalent dose of oral corticosteroids (eg, prednisone) at start of tapering or earlier, once sustained clinical improvement is observed. The lower bioavailability of oral corticosteroids needs to be considered.

6.3.4.7. Pulmonary Adverse Events

Pulmonary AEs including radiographic changes (eg, focal ground glass opacities and patchy infiltrates) indicative of drug-related pneumonitis have been observed in subjects receiving anti-PD-1 therapies. These pulmonary AEs were either asymptomatic or associated with symptoms such as dyspnea, cough, or fever. The initial occurrence of pulmonary AEs may be as early as after a single dose of anti-PD-1 therapies or delayed after prolonged therapy. Early recognition and treatment of pneumonitis is critical to its management (see [Table 22](#)). Subjects should be advised to seek medical evaluation promptly if they develop new-onset dyspnea, cough, or fever or if they have worsening of these baseline symptoms.

Table 22: Management of Pulmonary Adverse Events

For guidelines for delaying a dose, refer to Section 6.3.2 .	
Grade 1	Monitor for symptoms every 2-3 days; consider pulmonary and infectious-disease consult; re-image every 3 weeks Worsening: treat as \geq Grade 2
Grade 2	Monitor symptoms daily; re-image every 1-3 days; pulmonary and infectious-disease consultation; consider bronchoscopy and lung biopsy; consider hospitalization Immediately: start 1.0 mg/kg/d methylprednisolone IV or oral equivalent; prophylactic antibiotics Persistence for 2 weeks or worsening: treat as Grade 3-4 Improvement to \leq Grade 1 or baseline: taper steroids over at least 4 weeks
Grade 3-4	Hospitalize; pulmonary and infectious-disease consult; consider bronchoscopy and lung biopsy Immediately: 2-4 mg/kg/d methylprednisolone or IV equivalent; add prophylactic antibiotics; Persistence for 2 days or worsening: add immunosuppression (eg, infliximab, cyclophosphamide, IVIG, or mycophenolate mofetil) Improvement to \leq Grade 2: taper steroids over at least 6 weeks
General	Subjects on IV steroids may be switched to an equivalent dose of oral corticosteroids (eg, prednisone) at start of tapering or earlier, once sustained clinical improvement is observed. The lower bioavailability of oral corticosteroids needs to be considered.

6.3.4.8. Uveitis and Visual Complaints

Immune therapies have been uncommonly associated with visual complaints. Inflammation of components within the eye (eg, uveitis) is an uncommon, but clinically important, event. An ophthalmologist should evaluate visual complaints with examination of the conjunctiva, anterior and posterior chambers, and retina. Complaints of double vision should also prompt medical evaluation. In addition to ocular inflammatory events, a work-up should also consider pituitary inflammation as a cause. Additional eye toxicity guidance is provided in [Section 6.2.3.6](#). See [Table 23](#) for management guidelines.

Table 23: Management of Uveitis and Visual Complaints

For guidelines for delaying a dose, refer to Section 6.3.2 .	
Grade 1	Thorough eye examination
Grade 2	Topical corticosteroids should be considered Persisting despite topical steroids, treat as Grade 3-4
Grade 3-4	Thorough eye examination Systemic corticosteroids

6.3.4.9. Lipase/Amylase Elevations

Asymptomatic elevations in lipase and amylase have been reported in anti-PD-1 therapy studies in which systemic monitoring was used. Very few subjects reported associated symptoms (eg, abdominal pain) or radiographic findings (eg, stranding) consistent with pancreatitis. Thus, there does not seem to be clinical significance to the elevated laboratory values. The recommended management of anti-PD-1 therapy-related elevated lipase/amylase values centers around close observation. Physicians should ensure that subjects have no associated symptoms consistent with pancreatitis, such as abdominal pain. Corticosteroids do not seem to alter the natural history of lipase/amylase elevations. Laboratory values tend to fluctuate on a day-to-day basis and eventually return to baseline or low-Grade levels over the course of weeks, whether or not subjects receive corticosteroids. Asymptomatic elevations should be monitored approximately weekly.

6.3.4.10. Infection

Subjects with a documented infectious complication should receive oral or IV antibiotics or other anti-infective agents as considered appropriate by the treating investigator for a given infectious condition, according to standard institutional practice.

6.3.4.11. Treatment of Anti-PD-1 Infusion-related Reactions

Since cetrelimab contains only human immunoglobulin protein sequences, it is less likely to induce a hypersensitivity reaction. However, if such a reaction were to occur, it might manifest with fever, chills, rigors, headache, rash, pruritus, arthralgias, hypo- or hypertension, bronchospasm, or other symptoms. Management of IRRs is provided in [Table 24](#).

All CTCAE Grade 3 or 4 IRRs should be reported within 24 hours to the medical monitor and reported as an SAE if criteria are met.

Table 24: Management of Infusion-Related Reactions

Management and Follow-up of Infusion-Related Reactions. For guidelines for delaying a dose, refer to Section 6.3.2	
Grade 1	No intervention indicated; remain at bedside and monitor subject until recovery from symptoms. Consider diphenhydramine 50 mg (or equivalent) and/or paracetamol 325 to 1000 mg (acetaminophen) at least 30 minutes before additional study drug administration.
Grade 2	Stop infusion: start IV saline infusion; give diphenhydramine 50 mg (or equivalent) IV and/or paracetamol 325 to 1000 mg (acetaminophen); consider corticosteroids and bronchodilator therapy; remain at bedside and monitor subject until recovery from symptoms. Restart infusion at 50% of initial rate: if no further complications ensue after 30 minutes, the rate may be increased to 100% of the original infusion rate; monitor subject closely. Symptoms recur: stop and discontinue further treatment at that visit; administer diphenhydramine 50 mg IV, and remain at bedside and monitor the subject until resolution of symptoms. The amount of study drug infused must be recorded on the eCRF.
Grade 3-4	Stop infusion: start IV saline infusion; recommend bronchodilators, epinephrine 0.2 to 1 mg of a 1:1,000 solution for subcutaneous administration or 0.1 to 0.25 mg of a 1:10,000 solution injected slowly for IV administration, and/or diphenhydramine 50 mg IV with methylprednisolone 100 mg IV (or equivalent), as needed. Subject should be monitored until the investigator is comfortable that the symptoms will not recur. Study drug will be permanently discontinued. Investigators should follow their

	institutional guidelines for the treatment of anaphylaxis. Remain at bedside and monitor subject until recovery from symptoms. In the case of late-occurring hypersensitivity symptoms (eg, appearance of a localized or generalized pruritus within 1 week after treatment), symptomatic treatment may be given (eg, oral antihistamine, or corticosteroids).
General	Prophylactic medications (after initial event): diphenhydramine 50 mg (or equivalent) and/or paracetamol 325 to 1000 mg (acetaminophen) at least 30 minutes before additional study drug administrations; if necessary, corticosteroids (recommended dose: up to 80 mg of IV methylprednisolone or equivalent) may be used. Appropriate resuscitation equipment should be available in the room and a physician readily available during the infusion of study drug.

6.3.4.12. Monitoring During and After Study Drug Administration

Subjects should be carefully observed during cetrelimab infusions. Trained study staff at the clinic should be prepared to intervene in case of any IRRs occurring, and resources necessary for resuscitation (eg, agents such as epinephrine and aerosolized bronchodilator, also medical equipment such as oxygen tanks, tracheostomy equipment, and a defibrillator) must be available at bedside. Attention to staffing should be considered when multiple subjects will be dosed at the same time.

If an infusion-related reaction develops, then the infusion should be temporarily interrupted or slowed down. Guidelines outlined in Section 6.3.4.11 must be followed to manage IRRs.

Subjects should be monitored for at least 2 hours after the completion of the first infusion and may be discharged if considered clinically stable and all other study procedures have been completed. The investigator will determine the duration of safety monitoring for subsequent administrations.

6.4. Administration of Platinum Chemotherapy (Cisplatin or Carboplatin)

Refer to Section 6.4 of Appendix 2.

6.5. Toxicity Due to One Study Drug and Continuation of Treatment

The dose modification guidelines described in Section 6.2, Section 6.3, and Section 6.4.4 are to be used throughout both phases of the study, as applicable. If a subject experiences several toxicities and there are conflicting recommendations, the most conservative dose adjustment recommended should be followed (dose reduction appropriate to the most severe toxicity). The recommendation to discontinue study therapy may apply to all study drugs. However, in cases in which the investigator and the study sponsor agree that the observed drug-related AE leading to discontinuation was most probably related to 1 of the study drugs, continuation of therapy with the other study drug(s) is permitted after discussion with the medical monitor.

7. TREATMENT COMPLIANCE

The investigator or designated study personnel will maintain a log of the amount of study drug dispensed and returned. Drug supplies will be inventoried and accounted for throughout the study.

Subjects will receive instructions on compliance with study treatment at the Screening visit. A diary card will be given to the subject to record intake at home. On days when the subject visits the study center for dose administration or PK sampling, the investigator or designee will supervise

administration of the study drug and the exact time of administration will be recorded in the eCRF. During the course of the study, the investigator or designated study research staff will be responsible for providing additional instruction to reeducate any subject who is not compliant with the study drug schedule.

If appropriate, site visits may be replaced with telephone visits during a national disaster, with site visits resuming as soon as possible thereafter. Please refer to [Attachment 10](#) for additional guidance on study conduct for enrolled subjects during a national disaster.

8. CONCOMITANT THERAPY

Following Amendment 5, and after end of study data collection timepoint has been achieved, the eCRF will be closed and only concomitant therapies associated with an SAE must be reported through the company safety repository.

Therapies are to be recorded at the time of Screening (within 28 days prior to the first dose of study drug), throughout the study, and up to 100 days after the last dose of study drug in the appropriate section of the eCRF. Once a subject starts a subsequent systemic anticancer therapy, data collection will be limited to concomitant medications used to treat ongoing or newly developed Grade ≥ 2 immune-related AEs considered related to cetrelimab.

All therapies (prescriptions or over the counter medications) continued at the start of the study or started during the study and different from the study drug must be documented in the concomitant therapy section of the eCRF. Caution should be exerted for subjects taking anticoagulant therapies. Frequent monitoring for international normalized ratio (INR) is allowed at the treating physician's discretion.

The sponsor must be notified in advance, or as soon as possible thereafter, of any instances where prohibited medications are administered.

8.1. Permitted Medications

Throughout the study, investigators may prescribe concomitant medications or treatments (including nutritional support, correction of metabolic disorders, optimal symptom control, and pain management) deemed necessary to provide adequate supportive care. Concurrent use of hormones for non-cancer related conditions (eg, insulin for diabetes and hormone replacement therapy) is acceptable. Concomitant medications (eg, acetaminophen/paracetamol or diphenhydramine) deemed necessary by the investigator to provide adequate prophylaxis and management of IRRs are allowed. Refer to Section [6.3.4](#) for guidance on medications to manage immune-related toxicities.

In addition, the following medications may be administered during the study:

- Standard supportive care therapies (antiemetics, antidiarrheals, anticholinergics, antispasmodics, antipyretics, antihistamines, analgesics, antibiotics and other antimicrobials, histamine receptor [H2] antagonists or proton pump inhibitors, and other medications intended to treat symptoms or signs of disease) as clinically indicated, according to institutional standards and as deemed necessary by the investigator.

- Permitted antiemetics include: aprepitant, ondansetron, and dexamethasone
- Documented infectious complication should be treated with oral or IV antibiotics or other anti-infective agents as considered appropriate by the treating investigator for a given infectious condition, according to standard institutional practice.
- In general, growth factor support is permitted for the management of treatment-emergent hematological toxicity as recommended according to National Comprehensive Cancer Network/European Organization for Research and Treatment of Cancer ([NCCN/EORTC 2018](#)) guidelines. Primary prophylaxis is not permitted for subjects who are under evaluation for DLTs.
- Palliative radiotherapy: Localized radiotherapy for symptomatic control is permitted but should not include definitive radiation to target lesions.
- Chronic supportive therapies: Ongoing bisphosphonates and denosumab or other supportive therapies are permitted.

8.2. Prohibited Medications and Therapy

The following medications are prohibited during the study ([Table 25](#)). The sponsor must be notified in advance, or as soon as possible thereafter, of any instances in which prohibited therapies were administered. Other anticancer treatments are not allowed in this study.

Table 25: Prohibited Concomitant Medications and Therapies⁴

Antineoplastic Therapy

 • Cytotoxic chemotherapy (other than those under study in the appropriate cohort[s] of the study) • Biological therapy (including but not limited to: therapeutic antibodies and cytokines) • Radiation therapy¹ • Investigational agents
Immunotherapy

 • Immunotherapy for any indication • Live, attenuated vaccines (including but not limited to the following: measles, mumps, rubella, chicken pox, yellow fever, H1N1 flu, rabies, Bacillus Calmette-Guérin, and typhoid)².
Immunosuppressive Agents

 • Systemic corticosteroids (>10 mg prednisone per day or equivalent for over 5 days) other than those given for IRRs, as described in Section 6.3.4 should be avoided.³ 
 ○ Systemic glucocorticoids for any purpose other than to modulate symptoms from an event of clinical interest or for use as a premedication for chemotherapeutic agents specified in the protocol. • Methotrexate, cyclosporine, azathioprine, and TNF-α blockers.
Other
Colony-Stimulating Factors (CSFs): Routine primary prophylaxis is not permitted for subjects who are under evaluation for DLTs; For the use of CSFs after the DLT period ends, utilize (NCCN/EORTC 2018) guidelines.

Abbreviations: H1N1= Hemagglutinin Type 1 and Neuraminidase Type 1; IRRs= infusion-related reactions; TNF- α = tumor necrosis factor alpha

1. Palliative radiation therapy may be allowed after consultation and in agreement with the study sponsor.
2. Live, attenuated vaccines are prohibited 28 days prior to the first dose of study therapy and throughout study participation. Annual inactivated influenza vaccine is allowed.
3. Chronic (≥ 14 days) use of glucocorticoid for the clinical management of AEs is allowed. The use of physiologic doses of corticosteroids may be approved after consultation and in agreement with the study sponsor.
4. For further information regarding the interaction between cisplatin or carboplatin with other medicinal products (and other forms of interaction), please refer to the current approved label for cisplatin or carboplatin as applicable.

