Therapy with immuno-oncology agents such as cetrelimab can lead to specific irAEs that differ in nature, severity and duration as compared to AEs caused by agents with a different mode of action. Early recognition and management of these irAEs may mitigate more severe/subsequent toxicity. However, differential diagnoses including non-inflammatory etiologies as well as the impact of the underlying malignant disease and/or concomitant medication should be evaluated according to standard medical practice.

Management algorithms have been developed to assist investigators in assessing and managing specific irAEs following administration of nivolumab ([Knowles 2015](#)); ([Nivolumab 2016](#)) and pembrolizumab ([Keytruda® 2014](#)); ([Oken 1982](#)). These guidelines are presented below and should be followed for cetrelimab. In addition to the management algorithms provided in following sections, it is recommended that irAEs are managed according to the general treatment guidelines outlined for ipilimumab ([Ipilimumab 2015](#)). These guidelines recommend the following:

1. Subjects should be evaluated to identify any alternative etiology.
2. In the absence of a clear alternative etiology, all events of an inflammatory nature should be considered immune-related.

3. Symptomatic and topical therapy should be considered for low-Grade events.
4. Systemic corticosteroids should be considered for a persistent low-Grade event or for a severe event.
5. More potent immunosuppressants should be considered for events not responding to systemic corticosteroids (eg, anti-tumor necrosis factor agents or mycophenolate).

If delaying the dose is necessary to ameliorate a toxicity, follow the guidance in Section [6.3.2](#).

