6.3.4.1. Gastrointestinal Adverse Events

Diarrhea and colitis have been observed in subjects receiving anti-PD-1 therapies. Early recognition and treatment of diarrhea and colitis are critical to their management (see [Table 16](#)). Subjects should be advised to seek immediate medical evaluation if they develop new-onset diarrhea, blood in stool, or severe abdominal pain or if they have worsening of baseline diarrhea. In subjects with pre-existing diverticulosis and/or diverticulitis receiving concomitant medication with corticosteroids, nonsteroidal anti-inflammatory drugs, and opioid analgesics together with anti-PD-1 therapies, diverticular perforation has been observed.

Table 16: Management of Immune-Related Gastrointestinal Adverse Events

For guidelines for delaying a dose, refer to Section 6.3.2.	
Grade 1	Symptomatic treatment according to institutional standards Close monitoring; instruct subject to report worsening immediately and treat as Grade ≥2
Grade 2	≤5 days: Symptomatic treatment according to institutional standards >5 days or recurrence: 0.5–1.0 mg/kg/d methylprednisolone; consider prophylactic antibiotics; Persistence or worsening despite steroids >3 days: treat as Grade 3/4 Improvement to ≤Grade 1: taper steroids over at least 4 weeks, consider prophylactic antibiotics for opportunistic infections, resume study therapy per protocol
Grade 3–4	Immediately: 1.0–2.0 mg/kg/d methylprednisolone IV; consider prophylactic antibiotics and lower endoscopy Persistence >3 days or recurrence: add infliximab 5 mg/kg (if no contraindication such as perforation or sepsis) Improvement to ≤Grade 2 within ≤3 days: taper steroids over at least 4 weeks
General	The oral corticosteroid equivalent of the recommended IV dose may be considered for ambulatory subjects; the lower bioavailability of oral corticosteroids needs to be considered. Clinical caution should be exercised, for subjects receiving concomitant medications of corticosteroids, nonsteroidal anti-inflammatory drugs, or opioid analgesics. In addition, monitor for signs and symptoms of potential perforation, especially in subjects with known diverticular disease. Narcotics should be used with caution as pain medicines may mask the signs of colonic perforation.

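### Table 25 bans TNF-alpha blockers without an immune-related exception, yet Table 16 tells sites to give infliximab for steroid-refractory immune-related colitis

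*Protocol*

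**What the plan says.** **The ban.** Section 8.2 makes the contents of Table 25 off limits for the duration of the study. Under Immunosuppressive Agents, one bullet reads "Methotrexate, cyclosporine, azathioprine, and" and closes with TNF-alpha blockers. That bullet has no footnote and no qualifier.

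**The exceptions in the same box.** These cover steroids only. One steroid entry is worded "Systemic glucocorticoids for any purpose other than to modulate symptoms from an event of clinical interest", with a further allowance for chemotherapy premedication. Another steroid entry exempts infusion-related reactions handled under Section 6.3.4. Footnote 3 permits prolonged glucocorticoid use for treating adverse events.

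**The instruction.** Section 6.3.4 says of its algorithms: "These guidelines are presented below and should be followed for cetrelimab". Its general rules advise stronger immunosuppression for "events not responding to systemic corticosteroids (eg, anti-tumor necrosis factor agents or mycophenolate". In Table 16, when a Grade 3-4 gastrointestinal event persists more than 3 days or recurs, the step is to "add infliximab 5 mg/kg (if no contraindication such as perforation or sepsis". The Grade 2 row leads to the same place: "Persistence or worsening despite steroids >3 days: treat as Grade 3/4".

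**The link between the two.** Section 8.1, under permitted medications, refers the reader to Section 6.3.4 "for guidance on medications to manage immune-related toxicities". Section 8 adds: "The sponsor must be notified in advance, or as soon as possible thereafter, of any instances where prohibited medications are administered".

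**The concern.** Two current rules give opposite answers for the same drug in the same patient. The mandated colitis algorithm ends in infliximab once steroids have failed, and the prohibited list names infliximab's class without qualification.

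The steroid exceptions sharpen the problem. Table 25 allows one immunosuppressant class for treating adverse events and leaves the next bullet unqualified, so a literal reader could take the ban on TNF-alpha blockers as deliberate.

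Two things are at stake. First, an investigator with a deteriorating colitis patient has to work out which table governs. Second, a site that follows Table 16 correctly must notify the sponsor that it gave a prohibited drug, so proper use of the safety algorithm is recorded as a departure from the concomitant-therapy rules. Section 1.5.2 relies on these algorithms, including the gastrointestinal one, as a risk mitigation measure, so they should be free of internal conflict.

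**Working it through.** No figure in the plan is in dispute. The check compares the texts and then counts how far the conflict reaches.

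**Step 1. Does the instruction fall under the ban?** Infliximab is a TNF-alpha blocker. Table 25 bans that class by name, and Table 16 prescribes the drug at a stated dose. The overlap is direct.

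**Step 2. Does any exception in Table 25 reach it?**
- The infusion-reaction exemption sits on a systemic corticosteroid entry.
- The exemptions for events of clinical interest and for premedication sit on a systemic glucocorticoid entry.
- Footnote 3 covers glucocorticoids only.

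None applies to TNF-alpha blockers.

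**Step 3. Does stopping cetrelimab avoid the conflict?** No. Section 6.3.3 says that stopping cetrelimab does not automatically withdraw the subject, who may continue the other study treatment. The subject is still on study and the ban still applies.

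**Step 4. How many algorithms are affected?** Tables 16 to 23 are the eight immune-related management tables. Four name an immunosuppressive step beyond steroids:

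| Table | Event type | Named step after steroids | Conflict with the TNF-alpha line |
|---|---|---|---|
| 16 | Gastrointestinal | Infliximab only | Full |
| 17 | Hepatic | Mycophenolate, then other agents by local guideline | None by name |
| 21 | Neurological | Intravenous immunoglobulin or other institutional choice | None by name |
| 22 | Pulmonary | Infliximab as one of four examples | Partial; alternatives exist |

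Mycophenolate and intravenous immunoglobulin are not named under Immunosuppressive Agents in Table 25. The general rule in Section 6.3.4 offers mycophenolate beside anti-TNF agents, so the conflict there is also partial. Table 16 is the only one of the four that depends wholly on a banned class.

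**Step 5. How many planned subjects come under both rules?** Inputs are the planned numbers in the Synopsis: 90 subjects in Phase 2 randomised 1:1, so about 45 in Arm B; 30 in Phase 1b erdafitinib + cetrelimab; 40 in Phase 1b with platinum; 160 in total.

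- Cetrelimab-treated: 45 + 30 + 40 = 115, and 115 / 160 = 72%.
- The erdafitinib + cetrelimab cohort is also given as a range of 12 to 30. At the low end: 45 + 12 + 40 = 97, of a total 90 + 12 + 40 = 142, or 68%.

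These figures count subjects to whom both tables apply, not subjects who would need infliximab. That number cannot be derived because the protocol gives no rate of steroid-refractory colitis.

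**The case against.** The best counter-argument is that the protocol already answers the question. Section 8.1, under the heading for permitted drugs, sends the reader to Section 6.3.4 for immune-toxicity treatment. A specific, dosed, graded rescue step would ordinarily be read as governing over a generic class list. The four drugs in the Table 25 bullet also match exclusion criterion 18.1, which concerns background immunosuppression before the first dose, and the amendment history suggests the sponsor expected agents beyond steroids for severe immune toxicity. The intent to allow infliximab is fairly clear.

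The consequences are also light. The sponsor may be told after the drug is given, so no approval or delay is required. Section 10.2 does not list use of a prohibited drug as a reason to stop treatment or withdraw a subject. After Amendment 5 the protocol concerns only subjects still on treatment, so a correction now would reach few people.

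Much of this stands. It limits the seriousness, and it means the planned 115 should not be read as a count of people harmed. It does not remove the contradiction. A pointer to guidance is not an exception to a named ban, and nothing in the document sets an order of precedence. If the bullet was carried over from the entry criteria, the missing exception is an oversight, which supports correcting it. Subjects may continue cetrelimab after the data collection timepoint, and Appendix 4 still refers sites to Section 6.3, so the conflict remains live for them.

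**Conclusion.** The point holds. As written, Table 25 prohibits the only drug that Table 16 names after steroids for immune-related colitis, and no text reconciles the two. One of the four algorithms with a named post-steroid step is fully in conflict and one partly so. The two rules jointly cover about 115 of 160 planned subjects (about 97 of 142 at the low end of the Phase 1b range). How many would reach the infliximab step is unknown.

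The harm lies in conduct and classification: ambiguity at a rescue-treatment step, and protocol-directed care labelled as prohibited therapy. The text does not force a treatment delay. No effect on the response-rate analysis, sample size or error rates is claimed, and no connection is drawn to the Arm B death described in Section 1.5.2. The conclusion rests on infliximab belonging to the TNF-alpha blocker class and on reading Table 25 as applying throughout study participation, as Section 8.2 states. It should be corrected, though it does not threaten the trial's conclusions.

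**What to change.** Add an exception to the TNF-alpha blocker entry in Table 25, such as: *except when used to manage immune-related adverse events according to Section 6.3.4*. State in the same place that such use is not prohibited therapy and does not trigger the prohibited-medication notification. This parallels the exceptions the box already gives for corticosteroids.

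The cost is one line or footnote. It adds no procedure, visit or data item and changes no analysis.
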